Introduction. Malnutrition is recognized as a major concern by healthcare providers, as well as by patients, families, and caregivers. In a very recent survey, 28% of 1,035 patients, families and caregivers reported that malnutrition was a very significant problem, while 55% reported it was a somewhat significant problem in older adults 65 and older.²⁶ This response aligns with reports that up to 65% of older adults admitted to the hospital are malnourished (National Resource Center on Nutrition, Physical Activity, and Aging, 2015). Thus, it is essential to establish systematic malnutrition screening in the clinical setting and to develop intervention models and standards of nutritional care. The objective of this aim is to investigate the feasibility, fidelity and acceptability of a nutrition intervention protocol providing higher protein intakes before and after surgery in malnourished Veterans. To achieve the objective of this aim, we will test our working hypotheses that recruitment in clinic will have a high yield and that intervention fidelity (adherence, retention) and acceptability (attrition, patient satisfaction) will be predominantly satisfactory. The rationale for this aim is that successful completion of the proposed research will provide necessary knowledge to begin to identify feasible and acceptable interventions for community-dwelling Veterans who are preparing for surgical procedures. When the proposed studies for Aim 1.1 have been completed, it is our expectation that $\geq 75\%$ of patients approached for recruitment will agree to participate, $\geq 75\%$ of the time patients will adhere to the intervention, $\geq 80\%$ of the participants will remain in the study, and that $\geq 80\%$ of participants will find the intervention to be acceptable. Such findings would be of considerable importance, providing a patient-centered viewpoint that will inform the development of nutrition interventions that meet the standards and needs of high-risk Veteran Populations.

Specific Aim 1.2 – *To determine the effect size for planned future studies of enhanced protein supplementation in malnourished Veterans, with physical function as the primary outcome of interest. Of secondary interest are: biomarkers of inflammation (albumin, hsCRP, TNF- α , IL-6), dietary intake, hospital readmission, discharge location, length of skilled care, and ED admission, and physical activity.*

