Data management and quality control: We will employ REDCap (Research Electronic Data Capture) for data entry. Key components of this activity include data entry screen programming and database testing and validation. The database will include study default parameters and ranges for database, protocols, users, and access rights. Access and data entry to the database will be controlled by login permissions, and the database will be backed up daily, with full backups occurring weekly, and quarterly backups retained for perpetuity. The database will be routinely checked for data integrity and quality. In addition, since some data will require direct download from computerized databases (e.g. VA patient information, lab findings) a final relational database will be built to be used for analysis in SAS, combining data from all data sources. This process will include quality control, developing an appropriate query, validation, and justification procedures, auditing, developing a manual of procedures and documentation, interim reporting of data flow, and maintaining security and patient confidentiality of the data base. The analysis database derived from this source data will be de-identified. Identifying information will be viewed and managed only by the data manager and appropriately consented data collection staff.

Quality control procedures will be established for each component of the study. At each level of data management, and for each subject contact, strict adherence to VHA policy will be observed regarding HIPAA, IRB and other VHA patient quality controls. These procedures include not identifying any patient or provider on any of the reports generated from this study. All computer files will be password protected. Files containing names and addresses will have a separate password, will be accessible only to personnel who need to contact the subjects, and will be stored separately. Ultimately, a de-identified file appropriate for analysis will be produced for report generation and analysis. All analysis and Data management personnel are current with all VA mandated security training.

Aim 2.1 Analysis Plan:

Feasibility proportions for future screening and recruitment will be calculated at the end of the intervention using the following:

1. Proportion of patients recruited will be calculated as the number of patients deemed potentially eligible and contacted for enrollment divided by the total number of patients enrolled.

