 - Feasibility Hypothesis: $\geq 75\%$ of patients approached for recruitment will agree to participate

Fidelity proportions will be calculated for adherence and retention at the end of the intervention using the following:

1. Proportion adherent to nutrition intervention will be computed by the number of empty supplement containers divided by the number of possible supplement containers that could be consumed.

2. Proportion adherent to nutrition intervention will also be computed by the number of meals consumed that are 25 grams of protein divided by the number of possible meals that could be achieved. For the PoshControl arm, adherence will be assessed by the number of dietary changes they make based on the educational handout provided to them at baseline. These will be determined by using diet records for 3 days prior to surgery and 3 days following surgery. Diet food records are valid method for collecting dietary intake data and have been administered in Veteran populations.⁴² We have experience administering and analyzing this data.¹

- Adherence Hypothesis: $\geq 75\%$ of the time PeriHab participants will adhere to the intervention and $\geq 75\%$ of the time controls will show at least one recommended dietary change in their 3-day diet record

3. Proportion retention will be computed by dividing the number of retained subjects at the end of the intervention by the total number randomized into the study.

- Retention Hypothesis: $\geq 80\%$ of participants will remain in the study for the duration of the trial

We will calculate these rates of retention and adherence and their respective confidence intervals overall and by group. While non-powerful, we will assess if these rates differ by chi-square test of proportion and Poisson regression respectively. In a series of sensitivity tests, we will assess if adherence overall was impacted by demographic or symptomatic variables (such as chronic health conditions, living arrangements, surgery, functional status, and nutrition status).

Acceptability will be assessed by:

1. Calculating levels of attrition.

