- Patient satisfaction will be assessed by a brief 5-item questionnaire: a) satisfaction with participating in the study; b) satisfaction with directions on how and when to consume the protein supplement, c) satisfaction of the taste of the protein supplement, d) satisfaction with functional status after protein e) satisfaction with interactions with the registered dietitian. $\geq 80\%$ of participants will report satisfaction with participating in the study.

2. Qualitative semi-structured interviews in a subset of the participants. A qualitative analytical approach is well suited to exploring concepts related to a complex process (malnutrition and nutrition intervention). We anticipate we will achieve thematic saturation by enrolling 20 participants. The data in the interview transcripts will be coded using Atlas software. Perform the analysis using the skills obtained in my proposed coursework and with the assistance from my co-investigators. Data analysis will include summarizing the major topics of discussion, synthesizing recurring themes, and selecting exemplars of these themes from individual comments. In concert with the quantitative results, these data will be used to inform the design of a larger trial aimed at improving outcomes for older, malnourished Veterans.

- Patients will be selected using maximum variation purposive sampling including to include a mix of ages, genders, races, surgical procedures, and nutrition status.
- Each semi-structure interview will be conducted at the endpoint visit and will last approximately 15 minutes. The interviews will be conducted according to a script developed in close collaboration with my co-investigators.
- All interviews will be tape-recorded and transcribed. The interviewer will also take written notes to capture changes in emotion or enthusiasm related to the response to each question that will not be captured in transcribed reports.

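### Confidence intervals are planned for retention and adherence but not for recruitment or satisfaction, so two of the four feasibility expectations would be read on the point estimate alone

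*Combined protocol and SAP*

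**What the plan says.** The introduction to Specific Aim 1.1 describes the figures as working hypotheses to be tested and lists four: recruitment at least 75%, adherence at least 75%, retention at least 80%, and at least 80% "of participants will find the intervention to be acceptable".

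The matching analysis section is headed Aim 2.1 Analysis Plan. It treats the four as follows.

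- **Recruitment.** "Feasibility proportions for future screening and recruitment will be calculated at the end of the intervention". The proportion is defined as the "number of patients deemed potentially eligible and contacted for enrollment divided by the total number of patients enrolled", and beside it stands the hypothesis that at least 75% "of patients approached for recruitment will agree to participate". No interval is mentioned.
- **Adherence.** At least 75% "of the time PeriHab participants will adhere to the intervention", with a parallel statement for controls.
- **Retention.** At least 80% "of participants will remain in the study for the duration of the trial".
- **Acceptability.** Attrition, a five-item satisfaction questionnaire and qualitative interviews. The numeric statement is that at least 80% "of participants will report satisfaction with participating in the study". No interval is mentioned.

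The only sentence on precision is "We will calculate these rates of retention and adherence and their respective confidence intervals overall and by group". No sentence says how any of the four results will be compared with its threshold.

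**The concern.** Evaluating feasibility, fidelity and acceptability is the stated purpose of the pilot, and the results are meant to inform a larger trial. The plan already accepts that proportions of this kind need intervals, since it gives them for two of the four, and it offers no reason for leaving out the others.

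With neither an interval nor a reading rule, the natural report for recruitment and satisfaction is an observed percentage set beside 75% or 80%. A figure at or just above the threshold would then look like confirmation of the hypothesis, although the data would not exclude a rate well below it. For recruitment, that difference feeds directly into planning of the next trial.

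**Working it through.** **The plan's own figure.** No precision, power or error rate is stated for any Aim 1.1 expectation. The one design calculation, under Power Estimate, concerns physical function: a detectable standardized difference of 0.634 with 40 per group, 80% power and two-sided alpha 0.05. A two-sample t calculation gives 0.634, so it reproduces, but it does not bear on the feasibility proportions.

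**Inputs.**
- Thresholds: 75% for recruitment, 80% for satisfaction (Specific Aim 1.1; Aim 2.1 Analysis Plan).
- Completers: 84 (Design). Satisfaction is collected at T3 (Measures and Data Collection Points), so 84 is the direct denominator. Selection of Subjects can be read as 84 consented. With 80% retention that gives 0.80 × 84 ≈ 67 respondents, shown as the alternative.
- Number approached: not given. Central assumption 84/0.75 = 112. Also 84/0.80/0.75 = 140, within a range of 84 to 200.

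**Formulas.** The Wilson 95% interval for r out of n, with p = r/n and z = 1.96, is

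[p + z²/(2n) ± z·√(p(1−p)/n + z²/(4n²))] / (1 + z²/n).

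The chance of reaching the threshold is the exact binomial tail P(X ≥ r | n, true rate), where r is the smallest count at or above the threshold.

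**Recruitment, 84/112 = 75.0%.** (0.7672 ± 0.0820)/1.0343 = 66.2% to 82.1%.

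| Approached (assumed) | Result at threshold | Wilson 95% interval | Chance of 75% or more if true rate is 70% |
|---|---|---|---|
| 84 | 63/84 | 64.8% to 83.0% | 19.0% |
| 112 | 84/112 | 66.2% to 82.1% | 14.6% |
| 140 | 105/140 | 67.2% to 81.4% | 11.4% |
| 200 | 150/200 | 68.6% to 80.5% | 7.0% |

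**Satisfaction, 68/84 = 81.0%** (67/84 = 79.8% falls short). (0.8324 ± 0.0870)/1.0457 = 71.3% to 87.9%.

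| Respondents | Smallest result at or above 80% | Wilson 95% interval | Chance of 80% or more if true rate is 75% |
|---|---|---|---|
| 84 | 68/84 | 71.3% to 87.9% | 12.7% |
| 67 | 54/67 | 69.6% to 88.3% | 18.1% |

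For recruitment, the lower limit lies between 75 − 68.6 = 6.4 and 75 − 64.8 = 10.2 points below the threshold. For satisfaction, it lies 80 − 71.3 = 8.7 or 80 − 69.6 = 10.4 points below.

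**The recruitment ratio.** As written it is contacted divided by enrolled. With the central assumption that is 112/84 = 1.33. It cannot fall below 1 and cannot be compared with 75%. An interval for the stated hypothesis needs the reverse, 84/112 = 0.75.

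**The case against.** The strongest reply is that nothing in the documents declares a target met. The four figures are called expectations or hypotheses, and there is no pass/fail criterion and no go/no-go decision. The pilot is described as preliminary and preparatory. A reader might infer from the thresholds that the plan contains a success rule which these two results could wrongly pass. It does not, and the point does not rest on one. What stands is that the hypotheses are said to be tested, and that for these two only a bare proportion is provided to test them with.

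Second, retention and adherence have intervals but no rule linking them to their thresholds either. For example, 84/105 = 80.0% retained has an interval of 71.3% to 86.5%. That is correct, so the reading statement should cover all four.

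Third, acceptability does not rest on satisfaction alone. Attrition is the complement of retention and so is covered by the retention interval, and interviews add qualitative evidence. Also, the aim speaks of finding the intervention acceptable, while the analysis measures satisfaction with taking part. It would be too strong to say that acceptability as a whole is judged on one bare proportion. The gap is in its one directly reported percentage.

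Fourth, a formal rule based on the lower limit would be harsh. With 84 respondents it would need 75/84 (89.3%), and would be reached in 17% of trials if true satisfaction were 85%. A three-way label would be coarse: with 112 approached, every result from 76/112 (68%) to 92/112 (82%) has an interval containing 75%. This stands, and neither device is asked for.

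Finally, readers could compute these intervals from reported counts. That limits the seriousness of the gap, but it does not settle in advance how the investigators will interpret the results.

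**Conclusion.** The point holds as a gap in reporting and interpretation. Intervals are planned for two of the four headline proportions, and nothing says that any of the four will be read with its interval. For recruitment and satisfaction, a result on the threshold would be compatible with true rates about 6 to 10 points lower. A result at or above the threshold would occur in about 15% of trials if true recruitment were 70% (7% to 19% over 84 to 200 approached), and in about 13% if true satisfaction were 75% (18% with 67 respondents).

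These sizes rest on an assumed number approached, on 84 completers answering the questionnaire, and on independent responses. The conclusion does not change across the ranges shown. The gap does not affect the design, conduct or validity of the trial, and it does not show that the sample is too small for a pilot.

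**What to change.** In the Aim 2.1 Analysis Plan, extend the interval sentence to all four measures:

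- report recruitment as enrolled divided by contacted, correcting the inverted ratio, with a Wilson or exact 95% interval;
- report satisfaction overall and by arm, with the same type of interval;
- state the 95% level for the retention and adherence intervals too, since none is given;
- add that all four expectations will be interpreted with the interval and not on the point estimate alone.

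A lower-limit success criterion or a set of labels is optional and not needed to close the gap.

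The cost is a few sentences and slightly more analysis, with no new data. The consequence to accept is that a result on the threshold will be described as compatible with the expectation, not as having established it.

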Measures and Data Collection Points

| Measure | When Collected |
|------------------------------------|-----------------------|
| NSR-2002 | Baseline (T1), T2, T3 |
| PG-SGA | T1, T2, T3 |
| Nutrition Focused Physical Exam | T1, T2, T3 |
| Cognition | T1 |
| Medical History | T1 |
| Demographic | T1 |
| Anthropometrics | T1, T2, T3 |
| Comorbidity Status | T1 |
| Bristol Stool Chart | T1 |
| Short Physical Performance Battery | T1, T2, T3 |
| Handgrip strength | T1, T2, T3 |
| Biological Markers | T1, T2, T3 |
| Postoperative outcomes | T3 |

| | |
|---|----------------------------|
| Physical Activity | T1, T2, T3 |
| PROMIS and PROMIS GLOBAL QUESTIONNAIRES | T1, T2, T3 |
| Three-day Food Record | T1, T2, T3 |
| Protein Checklist | Daily |
| 24-Hour Dietary Recall | Weekly between time points |
| Participant Satisfaction Questionnaire | T3 |
| Participant Acceptability | T3 |

Risk/Benefit Assessment

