Any Veteran who contacts or is contacted by study staff will be told that their participation is voluntary, and they may choose not to answer any questions that they find too sensitive. Also, Veterans will be told that their participation will not affect their care at the VA. The study staff member will explain the study in detail, including compensation. No study procedures will begin until formal, written informed consent has been obtained.

Consent Process

On the day of their POSH clinic visit, potential participants identified we will be informed again that he or she is being recruited because he/she is having abdominal elective surgery and is a patient in the POSH clinic. The participant will be told that their participation is voluntary, and they may choose not to answer any questions that they find too sensitive. Also, Veterans will be told that their participation will not affect their care at the VA. The study staff member will explain the study in detail. The participant will be given as long as they need to read through the consent form and HIPAA Authorization. Study staff will answer all questions and concerns. No study procedures will begin until formal, written informed consent has been obtained.

Study Interventions

Caloric Intake and Monitoring Protocol for Both Arms: Caloric needs will be prescribed for each participant using an established standard of 30 to 35 kcal/kg⁴¹ at the VAPOSH clinic. To assure adequacy for all enrollees, calculated protein needs will be higher than the recommended 0.8 g/kg of body weight for both arms, **PoshControl** protein prescription = **1.0 g/kg of bodyweight** and **PeriHab** protein prescription = **1.6 g/kg of bodyweight**. Participants will be monitored by weekly phone calls during which study staff will ask the participant to recall their intake from the day before (24-hour dietary recall). This information will be used to ensure that both arms are meeting their calorie needs. If a participant in either arm has an inadequate intake they will be counseled on how to increase their current intake. Based on our previous assessment of similar populations, it is unlikely that the **PeriHab** arm will be able to meet the 1.6 g/kg of body weight protein prescription on their own and for that reason we are providing protein supplement to be consumed 3 times a day (as described below). The **PoshControl** arm will be given one ONS to consume every day prior to surgery.

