PeriHab Arm Protein Perihabilitation Protocol: The protein supplementation protocol provides for three daily supplements of 30 g of high quality protein in the form of a liquid nutritional supplement (30 g). Subjects will receive sample menus to help the participants incorporate the increased protein into their daily intake. Individually packaged portions of the liquid supplement will be supplied at the VAPOSH clinic visit (T1). Participants will be given a two-week supply of supplement. Included will be a printed check-off sheet for participants to record protein supplement use. The protein check-off sheet, three-day food record, Actigraph log, and lids from the protein drink will be turned in on the day of surgery (T2). Following their surgery, participants will be given an additional four week supply of the same supplement at discharge and the same materials as at the VAPOSH clinic visit (T1). The protein check-off sheet, three-day food record, Actigraph log, and lids from the protein bottles will be turned in at the follow-up appointment (T3).

Participants will be contacted weekly by study staff and queried with a standard set of open-ended questions designed to identify problems with compliance. Participants who are having difficulty will be provided additional counseling to ensure they are able to achieve 30 grams of high quality protein three times a day.

PoshControl Arm Protocol: Participants in the PeriControl arm will be asked to consume 1 ONS protein supplement per day prior to surgery. They will be provided education on the role of nutrition to prepare for and heal from surgery with the following main messages, 1) complications associated with malnutrition; 2) the benefits of good nutrition; 3) tips for dietary intake when not hungry; 4) easy food preparation; and 5) what to eat. The study Registered Dietitian will instruct the participant to follow the information on the handout. Study staff will call the PoshControl arm participants once a week to identify problems with compliance,

answer any questions and also remind participant to complete their 3-day food records. The ONS check-off sheet, three-day food record, and lids from the Ensure Plus bottles will be turned in on the day of surgery (T2). Four weeks following surgery, PoshControl participants will return for a follow-up appointment and will bring Ensure Plus checklist, three-day food record, and Actigraph log.

Adverse Events

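### The plan states a weekly-call reminder to complete the 3-day food record for PoshControl but none for PeriHab, although both arms' records feed dietary intake and record-based adherence

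*Combined protocol and SAP*

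**What the plan says.** The weekly calls are described in three places under Study Interventions.

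- **Both arms** (Caloric Intake and Monitoring Protocol): "Participants will be monitored by weekly phone calls during which study staff will ask the participant to recall their intake from the day before". The stated use is calorie adequacy: "This information will be used to ensure that both arms are meeting their calorie needs". Participants whose intake is inadequate are counselled. No food-record reminder is mentioned.
- **PeriHab** (Protein Perihabilitation Protocol): "Participants will be contacted weekly by study staff and queried with a standard set of open-ended questions designed to identify problems with compliance". Those in difficulty receive further counselling towards the protein goal. No food-record reminder is mentioned.
- **PoshControl** (Arm Protocol): weekly calls look for compliance problems and also "answer any questions and also remind participant to complete their 3-day food records".

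The table of measures schedules the 3-day food record at T1, T2 and T3 without distinguishing the arms, and both arm protocols list it among the items handed in at T2 and T3. The Aim 2.1 Analysis Plan (fidelity, item 2) defines PeriHab meal adherence as a share of meals at 25 g of protein, and control adherence by dietary changes. It then says: "These will be determined by using diet records for 3 days prior to surgery and 3 days following surgery". The adherence target is at least 75% in each arm. Specific Aim 1.2 lists dietary intake as a secondary outcome.

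**The concern.** A prompt to complete an outcome record should not depend on randomised arm. If it does, completeness can differ by arm for a reason the trial itself created. If PeriHab participants who fail to return the record are also the less adherent ones, meal adherence among returners overstates the arm's true figure against its 75% target. The between-arm comparison of dietary intake would then rest on two differently selected groups. Fidelity is one of the pilot's main questions, so its adherence figures should not carry an avoidable difference in data collection. The Aim 2.1 plan does not say how unreturned records enter the adherence proportion.

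**Working it through.** **Comparison of the texts.** The documents contain no figure on record return, so the point rests first on what each text states.

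| Call content stated | PoshControl | PeriHab |
|---|---|---|
| 24-hour recall, intake counselling (both-arms paragraph) | yes | yes |
| Compliance problems | yes | yes |
| Reminder to complete the 3-day record | yes | not stated |
| 3-day record handed in at T2 and T3 | yes | yes |

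The T1 record belongs to baseline and precedes the weekly calls, so only the T2 and T3 records are exposed.

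**Illustration of size.** Inputs:

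- From the documents: 42 participants per arm; 75% adherence target.
- Assumed: true mean PeriHab meal adherence 70%, SD 20 points; record return 70% without a reminder and 85% with one; correlation r between adherence and the tendency to return the record of 0, 0.3 or 0.5.
- Also assumed: people who return no record drop out of both numerator and denominator.

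Expected records: 42 × 0.70 = 29.4, about 29, without a reminder; 42 × 0.85 = 35.7, about 36, with one.

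Let a latent normal variable govern return, with p the proportion returning and c the normal quantile at 1 − p. Then

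observed mean ≈ 70 + r × 20 × φ(c)/p

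where φ(c)/p is 0.497 at p = 0.70 and 0.274 at p = 0.85. Simulation with beta-distributed adherence of the same mean and SD agrees with this formula to within 0.2 points. The simulated values are:

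| r | Observed at 70% return | Observed at 85% return | Due to missing reminder | Remaining with reminder |
|---|---|---|---|---|
| 0 | 70.0% | 70.0% | 0 | 0 |
| 0.3 | 73.0% | 71.7% | 73.0 − 71.7 = 1.3 | 71.7 − 70 = 1.7 |
| 0.5 | 75.1% | 72.9% | 75.1 − 72.9 = 2.2 | 72.9 − 70 = 2.9 |

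The formula gives the same reminder effect: 0.3 × 20 × (0.497 − 0.274) = 1.3 and 0.5 × 20 × (0.497 − 0.274) = 2.2 points.

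For scale, the standard error of a mean from 29 records is 20/√29 = 3.7 points, larger than the reminder effect.

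**The power statement.** The plan's detectable standardised difference of 0.634 (40 per group, 80% power, two-sided 0.05) reproduces as 0.6343 with the two-sample t-test. It concerns physical function and does not depend on food records.

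**The case against.** The strongest reply is that the PeriHab side is an inference from silence. The arm-specific text is plainly not a full list of call content, because the 24-hour recall appears only in the both-arms paragraph. The call script is not in the documents, and staff may remind everyone. This stands as a limit. A reader might infer that PeriHab calls are confined to supplement compliance and that PeriHab records are entirely unprompted. The documents do not support that: PeriHab participants receive the record materials again at discharge, hand records in at scheduled visits, and both arms are paid by time point. What the documents do support is narrower: the reminder is written down for one arm and not for the other.

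A reader might also infer that the missing reminder costs 3 to 5 points and can carry a true 70% up to the target. Those figures are the whole non-return bias at 70% return, 73.0 − 70 = 3.0 and 75.1 − 70 = 5.1. More than half of each would remain after the fix, and 75% is reached only at r = 0.5. Nothing in the documents shows that non-returners adhere less.

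Other sources also limit the dependence on these records. PeriHab adherence is first measured by empty containers, a daily protein checklist exists, and the 24-hour recall is prompted in both arms. The recall is a partial cross-check on intake, although its stated purpose is monitoring calorie needs. For intake, the mixed models give some protection if data are missing at random.

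Finally, the sentence naming diet records as the source follows directly after the control-arm measure and may refer to that alone. This carries less weight: counting meals at 25 g needs meal-level intake data, and the diet record is the only such source that the adherence section names.

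**Conclusion.** The point holds as a minor one. As written, prompting for a record that feeds a secondary outcome and record-based adherence differs by arm at T2 and T3. Under the assumptions shown, the missing reminder accounts for about 1.3 to 2.2 points of upward shift in observed PeriHab meal adherence, and for none if return is unrelated to adherence. The size and direction of any real bias cannot be derived from the documents, for adherence or for the between-arm intake comparison. The container count, the 24-hour recall, SPPB and the power statement are unaffected. Confidence is high on the difference in wording and low on its numerical effect.

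**What to change.** State the same food-record reminder for both arms, in the protocol's both-arms paragraph and in one common weekly-call script. Report the number and proportion of 3-day records returned, by arm and visit, beside the record-based adherence and dietary-intake results.

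The cost is one sentence in the protocol and one line in the call script, since both arms are already called weekly. If enrolment is complete, the reporting step is still possible and shows whether return differed. The reminder makes prompting equal but does not remove bias from records that remain unreturned, which is why return should be reported as well.
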